8.4 Listings

A Listing of Partial Seizures Occurrence Recorded on Daily Record Cards presents for subjects in ES for adjunctive therapy:

- Age category
- Site-Subject Number
- Study Visit
- Collection Date
- Number of Partial Seizures

Same listing will be repeated for subjects in ES for monotherapy therapy.

A Listing of Seizures Count by Type of Seizures for subjects in ES for adjunctive therapy:

- Age category
- Site-Subject Number
- Analysis Visit
- Seizure Type (IA, IB, IC, II, III)
- Number of Partial Seizures

Same listing will be repeated for subjects in ES for monotherapy therapy.

A Listing of Partial Seizure Frequency per Week and Percent Reduction of Partial Seizures, as Recorded on Daily Record Cards in FAS_A:

- Age category
- Site-Subject Number
- Retrospective + Selection Period Baseline Value

- Value / Reduction at Visit 4 (Analysis Visit 1)
- Value / Reduction at Visit 5 (Analysis Visit 2)
- Value / Reduction at Visit 6 (Analysis Visit 3)

Same listing will be repeated for subjects in FAS_M.

A Listing of Partial Seizure Frequency per Week and Percent Reduction from Baseline, as Recorded on Daily Record Cards for subjects in FAS_A:

- Age category
- Site-Subject Number
- Analysis Visit Number
- Study Visit
- Baseline Seizure Frequency per Week
- Seizure Frequency per Week at Visit
- Result
- Percent Reduction

Same listing will be repeated for subjects in FAS_M.

The following listings based on the 48h video-EEG will only be applicable to the subjects enrolled prior to Protocol Amendment 3:

A Listing Video EEG Part 1 presents for subjects in FAS_A:

- Age category
- Site-Subject Number
- Study Visit
- Start date/time monitoring
- Stop date/Time monitoring
- Total connect time
- Type of EEG performed
- If other

Same listing will be prepared for subjects in FAS_M.

A Listing Video EEG Part 2 presents for subjects in FAS_A:

- Age category
- Site-Subject Number
- Study Visit
- Was sleep included
- EEG pattern
- Spasms present

Same listing will be prepared for subjects in FAS_M.

A Listing Video EEG Number of Seizures presents for subjects in FAS_A:

- Age category
- Site-Subject Number
- Study Visit

- Non-IS seizures present
- Number of electrographic seizures (Partial Onset Seizure only)
- Number of electro-clinical seizures (Partial Onset Seizure only)
- Number of partial onset seizures (ILAE code I)
- Number of primary generalized seizures (ILAE code II)
- Number of primary generalized seizures (ILAE code II)

Same listing will be prepared for subjects in FAS_M.

A Listing Video EEG Number of Clusters presents for subjects in FAS_A:

- Age category
- Site-Subject Number
- Study Visit
- Non-IS Seizures Present
- Number of Partial Onset Seizures (ILAE code I)
- Number of Generalized Onset Seizures (ILAE code II)
- Number of Unclassified Epileptic Seizures (ILAE code III)

Same listing will be prepared for subjects in FAS_M.

A Listing Average Daily Frequency (ADF) and Percent Reduction of Partial Seizures as Measured by 48 hour Video-EEG presents for subjects in FAS_A:

- Age category
- Site-Subject Number
- Study Visit
- Number of Partial Seizures
- Average Daily Frequency
- Percent Reduction in Average Daily Frequency

Same listing will be prepared for subjects in FAS_M.

A Listing Average Daily Frequency (ADF) and Percent Reduction of Electro-Clinical Partial Seizure Frequency as Measured by 48 hour Video-EEG presents for subjects in FAS_A:

- Age category
- Site-Subject Number
- Study Visit
- Number of Electro-Clinical Partial Seizures
- Average Daily Frequency
- Percent Reduction in Average Daily Frequency

Same listing will be prepared for subjects in FAS_M.

A Listing Average Daily Frequency (ADF) and Percent Reduction of Partial Seizures, as Recorded on Daily Record Cards presents for subjects in FAS_A:

- Age category
- Site-Subject Number

- Analysis Visit number (Week number)
- Result
- Percent reduction

Same listing will be prepared for subjects in FAS_M.

9 PHARMACOKINETICS AND PHARMACODYNAMICS

Results of observed plasma concentrations and dose-normalized LEV plasma concentrations will be presented. Listings will be presented for subjects on adjunctive therapy and for subjects on monotherapy, separately.

9.1 Pharmacokinetics

9.1.1 Definitions and Derivations

For the calculation of descriptive statistics, a LEV plasma concentration below the lower limit of quantification (LLOQ) will be substituted by LLOQ/2.

Dose-normalized (to 10mg/kg for aged subjects of 6 months and above, or 7mg/kg for age less than 6 months) LEV plasma concentrations are derived as follows:

Dose-normalized LEV plasma concentrations = LEV observed plasma concentration / actual dose given (mg/kg) \times 10 (mg/kg) or 7 (mg/kg).

9.1.2 Tables and Figures

Descriptive statistics of LEV observed and dose-normalized plasma concentrations will be summarized per defined time window post-dose by age category (1 month \leq Age $<$ 6 months, 6 months \leq Age $<$ 1 year, 1 year \leq Age $<$ 2 years, 2 years \leq Age $<$ 4 years) and dose level per administration (10mg/kg, 20mg/kg, 30mg/kg in aged subjects of 6 months and above, 7mg/kg, 14mg/kg, 21mg/kg in aged subjects less than 6 months) in PK-PPS_A and PK-PPS_M. The statistics are calculated only if at least 2/3 of the individual data at a specific sampling point are above or equal to the LLOQ.

Scatter plots of LEV observed plasma concentrations vs. time after last dosing will be presented by age category and dose level. Scatter plots for LEV observed plasma concentrations vs time after last dosing by dose level will be superposed with different symbols in a single graph for each age category.

Scatter plots of LEV observed plasma concentrations vs. time after last dosing will be presented by age category and dose group. Scatter plots for LEV observed plasma concentrations vs time post dose by dose group will be superposed with different symbols in a single graph for each dose group. The dose groups are defined as:

- low dose group, 7mg/kg in aged subjects less than 6 months and 10mg/kg in aged subjects of 6 months and above;
- middle dose group, 14mg/kg in aged subjects less than 6 months and 20mg/kg in aged subjects of 6 months and above;

- high dose group, 21mg/kg in aged subjects less than 6 months and 30mg/kg in aged subjects of 6 months and above

Scatter plots of LEV dose-normalized plasma concentrations vs. time after last dosing will be presented by age category and dose level. Scatter plots for LEV dose-normalized plasma concentrations vs time after last dosing by dose level will be superposed with different symbols in a single graph for each age category.

Another scatter plot for LEV dose-normalized plasma concentrations vs time after last dosing will be presented by age category and AED category with different symbols in a single graph.

Scatter plots for LEV dose-normalized plasma concentrations vs time post dose by age category will be superposed with a scatter plot for LEV dose-normalized plasma concentrations vs time post dose in N01223 with different symbols in a single graph. Dose-normalization of LEV plasma concentrations in N01223 will be performed to 10mg/kg for a subject with a body weight less than 50kg and to 500mg for a subject with a body weight more than or equal to 50kg.

In addition, scatter plots for LEV dose-normalized plasma concentrations vs time post dose will be superposed with simulated LEV plasma concentration-time profiles based on the population PK model established in N01288 by age category. The data of LEV plasma concentrations and times in N01223 and N01288 are provided from data management group in UCB.

9.1.3 Listings

A subject data listing LEV Plasma Concentration Monitoring will present for subjects on adjunctive therapy and for subjects on monotherapy, separately:

- Treatment Group
- Region/Country/Site-Subject Number
- Gender/Age(years)/ Weight(kg)
- Visit
- Not Done (with a flag ‘N’)
- Last Study Medication prior to Blood Sampling Datetime (YYYY-MM-DDThh:mm)/ Relative Day
- Blood Sampling Date time (YYYY-MM-DDThh:mm:ss)/Relative Hours to Last Medication
- Last Dosage (mg/intake)
- Plasma LEV Concentration (μ g/ml)
- Time Window [-0 (Just before dosing), >0-1, >1-2, >2-4, >4-8, >8-12, and >12 hours post dosing]

- Dose Normalized Plasma Level ($\mu\text{g}/\text{ml}$): equivalent to 10mg/kg/administration for aged subjects of 6 months and above or 7mg/kg/administration for aged subjects less than 6 months

9.2 Pharmacodynamics

Not applicable.

10 SAFETY ANALYSES

Summary tables and listings will be presented for subjects on adjunctive therapy and for subjects on monotherapy, separately.

Summaries will be presented for: AEs, ECG data, vital signs and weight (continuous) data, and PCS data.

Safety data will be summarized for the Safety Sets, see [Section 3.5.2](#).

10.1 Extent of Exposure

The duration of exposure to LEV, as defined in [Section 3.2.7](#), will be summarized as a continuous parameter (in days). Descriptive statistics for the duration of exposure to study medication in days will be presented by age category and overall. Handling of missing study medication data is described in [Section 4.2.4](#).

The following listings will be provided: study medication administration and exposure to study medication.

10.1.1 Definitions and Derivations

Duration in days of exposure to study medication is calculated as:

Start date = Date of first administration of study medication

End date = Date of last administration of study medication

- A) Start Date (Morning) and End Date (Evening) then Duration=End date - Start date + 1
- B) Start Date (Morning) and End Date (Morning) then Duration=End date - Start date + 0.5
- C) Start Date (Evening) and End Date (Evening) then Duration=End date - Start date + 0.5
- D) Start Date (Evening) and End Date (Morning) then Duration=End date - Start date.

Note: The date of the first and last administration of study medication is recorded on the “First Administration” and the “Study Termination” eCRFs, respectively.

Note: Missing values for date of last administration of study medication are imputed as specified in [Section 4.2.4](#).

The exposure duration in days for a period is assumed to be equal to the duration of the respective period except for the Down-titration Period. For the Down-titration Period the exposure duration is calculated as:

Date of last administration of study medication – Date of first day of period +1.

If date of last administration of study medication is missing, the last complete administration date will be used.

For start and end dates of periods see [Section 2.3.1](#) and [Section 5.1.1.4](#) .

Details on study medication administration are recorded on the “Study Medication Administration – IV” and “Study Medication Administration – Dry Syrup” eCRFs.

The modal dose is calculated using the daily dose (morning dose + evening dose). If there are tied cases, the later dose will be the modal dose.

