3.2.1.2 End Date of the First/Second Period

A subject is regarded to have started/ended a period as described below. For this, the start dates and end dates of study periods for each subject are defined in the following sections.

3.2.1.2.1 Subjects enrolled prior to Protocol Amendment 3 who are not 48h video-EEG Failures and subjects enrolled according to Protocol Amendment 3

3.2.1.2.1.1 First period

Selection Period:

- Start: Day of Visit 1
- End:
 - Subject does not discontinue from study: 1 day before Visit 3, or
 - Subject discontinues from study: “Date of last contact with Subject” on “Study Termination, Screen Failure Packet” CRF.

Evaluation Period (only if subject does not discontinue before or at Visit 3):

- Start: Day of Visit 3
- End:
 - First of:
 - Day of Visit 6, or
 - Day of first Early Discontinuation Visit.

For subjects who do not enter the Second Period:

Down-Titration Period (only when subject is not on minimum dose):

- Start: 1 day after Day of End of Evaluation Period
- End: Day of Last Early Discontinuation Visit; if Day of Last Early Discontinuation Visit is missing, the date of last dose of study medication will be used

Followed by

Safety Follow-Up Period (safety follow-up visit will take place when subject is 2 weeks off study drug, ie, on 0mg/kg dose):

- Start: 1 day after Day of End of Down-Titration Period or 1 day after Day of End of Evaluation Period
- End: Day of Safety Follow-Up Visit

3.2.1.2.1.2 Second Period

Maintenance period:

- Start: 1 day after Day of Visit 6
- End: First of:
 - Day of first Early Discontinuation Visit, or
 - Day of End of Study*

- * Day of End of Study as determined by sponsor, connected to market approval or completion of development of LEV in subjects 1 month to <4 years

Down-Titration Period (only when subject is not on minimum dose):

- Start: 1 day after Day of End of Maintenance Period
- End: Day of Last Early Discontinuation Visit; if Day of Last Early Discontinuation Visit is missing, the date of last dose of study medication will be used

Followed by

Safety Follow-Up Period (safety follow-up visit will take place when subject is 2 weeks off study drug, ie, on 0mg/kg dose):

- Start: 1 day after Day of Down-Titration Period or 1 day after Day of End of Maintenance Period
- End: Day of Safety Follow-Up Visit

For subjects who did not discontinue from Maintenance Period:

- The end date will be captured on “study termination” CRF.

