3.2.1.2.2 Subjects enrolled prior to Protocol Amendment 3 who are 48h video-EEG Failures

3.2.1.2.2.1 First period

Selection Period:

- Start: Day of Visit 1
- End:
 - Subject dose not discontinue from study: 1 day before Visit 6, or
 - Subject discontinues from study: “Date of last contact with Subject” on “Study Termination, Screen Failure Packet” CRF.

3.2.1.2.2.2 Second Period

For 48h video-EEG failures, the data will be re-mapped according to Table 3-2 and will be included in the efficacy and safety analysis.

Dose Adjustment Period (only if subject does not discontinue at Visit 2):

- Start: Day of Visit 6
- End: First of:
 - Day of Visit 9, or
 - Day of first Early Discontinuation Visit

1. For subjects who discontinued during the Dose Adjustment Period:

Down-Titration Period (only when subject is not on minimum dose):

- Start: 1 day after Day of End of Dose Adjustment Period
- End: Day of Last Early Discontinuation Visit; if Day of Last Early Discontinuation Visit is missing, the date of last dose of study medication will be used

Followed by

Safety Follow-Up Period (safety follow-up visit will take place when subject is 2 weeks off study drug, ie, on 0mg/kg dose):

- Start: 1 day after Day of Down-Titration Period or 1 day after Day of Dose Adjustment Period
- End: Day of Safety Follow-Up Visit

2. For subjects who did not discontinue during the Dose Adjustment Period:

Maintenance Period:

- Start: 1 day after Day of Visit 9
- End: First of:
 - Day of first Early Discontinuation Visit, or
 - Day of end of study*

* Day of end of study as determined by sponsor, connected to market approval or completion of development of LEV in subjects 1 month to <4 years

3. For subjects who discontinue from maintenance period:

Down-Titration Period (only when subject is not on minimum dose):

- Start: 1 day after Day of End of Maintenance Period
- End: Day of Last Early Discontinuation Visit; if Day of Last Early Discontinuation Visit is missing, the date of last dose of study medication will be used

Followed by

Safety Follow-Up Period (safety follow-up visit will take place when subject is 2 weeks off study drug, ie, on 0mg/kg dose):

- Start: 1 day after Day of End of Down-Titration Period or 1 day after Day of End of Maintenance Period
- End: Day of Safety Follow-Up Visit

4. For subjects who did not discontinue from Maintenance Period:

- The end date will be captured on “study termination” CRF.

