3.2.7 Exposure to Study Medication

The date of first dose of study medication is defined as the first study medication dose date according to the First Administration CRF.

The date of last dose of study medication is defined as the last dose of study medication reported on the standard Trial Termination CRF.

The number of days of exposure is defined as the stop date minus the treatment start date +1 day. Days with unknown or zero dosing which occur prior to the last dose of study medication in the study will be included in the calculation.

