5.1.1.5 Duration of a Period

The duration of a period is not shown in context of disposition. The duration of a period is used as the duration of exposure to study medication, see [Section 3.2.7](#).

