7.1 Definitions and Derivations

Since derivations for compliance is connected to derivations for exposure, derivation to both topics are described here.

Date of first dose of study medication is documented in the “First Administration” CRF.

Missing values for date of last administration of study medication are imputed as specified in [Section 4.2.4](#).

Details on study medication administration are recorded on the CRFs: First Administration; Study Medication Administration – Dry Syrup; and Study Medication Administration – IV.

Overall compliance with Levetiracetam, administered once in the morning and once in the evening, will be examined for subjects whose total study medication administration and first and last days of treatment in the first and/or second period are known:

- First Period, Treatment compliance (%) will be calculated as follows:

$$\text{Compliance (\%)} = \frac{\sum_{\text{first day}}^{\text{last day}} (\text{\# of actual administrations per day})}{\text{total \# of administrations planned during the first period}} \times 100$$

where “total # of administrations planned during the first period” is equal to the total number of administrations planned during first administration of study medication to last planned administration in Evaluation Period, or day of discontinuation, which will be calculated as the duration of Evaluation Period in days $\times 2$. In consideration of whether the first administration is taken in the morning or in the evening, please see [Section 10.1.1](#).

- Second Period, Treatment compliance (%) will be calculated as follows:

$$\text{Compliance (\%)} = \frac{\sum_{\text{first day}}^{\text{last day}} (\text{\# of actual administrations per day})}{\text{total \# of administrations planned during the time the subject was in second period}} \times 100$$

where “total # of administrations planned during the time the subject was in the second period” is equal to the total number of administrations planned during first planned administration of study medication and last planned administration in Maintenance Period, or day of discontinuation, which will be calculated as the duration of Maintenance Period in days $\times 2$. In consideration of whether the first administration is taken in the morning or in the evening, please see Section 10.1.1.

- Overall Period, Treatment compliance (%) will be calculated as follows:

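### By-period exposure of a child who stops dosing before the first Early Discontinuation Visit runs to the visit, not the last dose, and an untapered child above the minimum dose gets negative Down-Titration exposure

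*SAP*

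**What the plan says.** Four SAP rules act together.

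- **Period end.** For a child who leaves early, SAP 3.2.1.2 ends the Evaluation, Dose Adjustment or Maintenance Period at the "Day of first Early Discontinuation Visit". The last dose is not an end point.
- **Period exposure.** SAP 10.1.1: "The exposure duration in days for a period is assumed to be equal to the duration of the respective period except for the Down-titration Period". SAP 5.1.1.5 repeats it: "The duration of a period is used as the duration of exposure to study medication". Whole-study exposure, by contrast, stops at the last dose (SAP 3.2.7 and 10.1.1), and "The date of last dose of study medication is defined as the last dose of study medication reported on the standard Trial Termination CRF".
- **Down-Titration.** SAP 3.2.1.2 opens it by dose level alone: "Down-Titration Period (only when subject is not on minimum dose". It starts the day after the preceding period ends; for the earlier video-EEG failures the line reads "Start: 1 day after Day of End of Dose Adjustment Period". It ends on the "Day of Last Early Discontinuation Visit; if Day of Last Early Discontinuation Visit is missing, the date of last dose of study medication". Its exposure under SAP 10.1.1 is the last dose date minus the period's first day, plus 1, with no lower limit.
- **Period compliance.** SAP 7.1 counts planned administrations in the First Period up to the "last planned administration in Evaluation Period, or day of discontinuation, which will be calculated as the duration of Evaluation Period in days", times 2. The Second Period rule is parallel.

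The protocol provides for stops without a taper. Protocol 6.3.1 requires immediate discontinuation for certain liver findings, and Protocol 5.1.2 exempts children withdrawing at the minimum dose.

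**The concern.** The SAP treats the last dose as the end of exposure for the whole study but uses a visit date for each period. When dosing stops before that visit, the off-drug days in between are booked as exposure. For an untapered child above the minimum dose, the SAP also creates a period that was never dosed and applies a formula that can return a negative number of days.

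The results would appear in the by-period exposure listing (SAP 10.1.3), the Study Periods listing (SAP 5.1.3) and the by-period compliance table and listing (SAP 7.1 to 7.3). SAP 5.1.1.4 uses the same period dates to decide who started a period. Compliance is grouped at 80%, the lower limit for persistent noncompliance in Protocol 7.7. A child who took every dose up to an instructed stop could therefore be shown as noncompliant.

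**Working it through.** The documents state no figure on this point, so the date rules were applied directly.

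**Inputs.** S is the first day of the period: Day 1 for Evaluation, the day after Visit 6 for Maintenance (SAP 3.2.1.2). L is the day of the last dose, E the day of the first EDV, and g = E − L. The documents do not give g; the values below are illustrations. Assumed: morning first dose, evening last dose, none missed up to L. Days on drug are d = L − S + 1.

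**Formulas.**

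1. SAP period exposure = E − S + 1 = d + g, an overstatement of g. Under the half-day cases B to D of SAP 10.1.1 the difference is g + 0.5 to g + 1.
2. Down-Titration starts on E + 1, so its exposure is L − (E + 1) + 1 = −g. With a single EDV the period ends on E, one day before it starts.
3. SAP period compliance = 2d / [2(d + g)] = d / (d + g), which is below 80% when g > d/4.

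**Evaluation Period (S = 1, d = L).** The Down-Titration column is for an untapered child above the minimum dose.

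| Last dose | First EDV | g | SAP exposure | Days on drug | Down-Titration exposure | SAP 7.1 compliance |
|---|---|---|---|---|---|---|
| Day 22 | Day 22 | 0 | 22 | 22 | 0 | 100% |
| Day 22 | Day 23 | 1 | 23 | 22 | −1 | 22/23 = 95.7% |
| Day 22 | Day 29 | 7 | 29 | 22 | −7 | 22/29 = 75.9% |
| Day 29 | Day 37 | 8 | 37 | 29 | −8 | 29/37 = 78.4% |
| Day 7 | Day 9 | 2 | 9 | 7 | none opened | 7/9 = 77.8% |

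A child stopping on Day 7 under 2-week titration is still on the starting dose, so no Down-Titration Period is opened.

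**Maintenance Period (S = Day 44, Visit 6 on Day 43).** A last dose on Day 100 gives d = 57. With g = 7, exposure is 64 days and compliance 57/64 = 89.1%. With g = 14, they are 71 days and 57/71 = 80.3%. Crossing the 80% line is thus mainly a matter of stops soon after a period begins.

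**Sum over periods.** Above the minimum dose without a taper, (d + g) + (−g) = d, so the total is right although both parts are wrong. At the minimum dose the sum is d + g, for example 9 days against 7.

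**What the compliance figure means.** Take L = 22 and E = 29. The 7 days in between carry 14 administrations in the denominator.

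- Instructed stop: those 14 were not planned. The right figure is 44/44 = 100%, and 44/58 = 75.9% understates it.
- The family stopped giving drug that was still prescribed: the 14 were planned and missed, and 75.9% is correct.

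**The case against.** The protocol default protects most early stoppers. Protocol 7.2 calls for down-titration on early discontinuation, and Table 5-3 dispenses drug at EDV Week 0. A child who follows this is dosed after the first EDV and gets correct values. Negative Down-Titration exposure needs an untapered stop above the minimum dose, with a liver-injury stop the clearest route, in a study planning 38 children for the primary analysis and 10 on monotherapy. This stands: few children are likely to be affected.

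The exposure rule is also a declared assumption, and the exposure listing prints first and last dose dates, so a reader could spot the mismatch. A programmer might drop an impossible period. But the SAP gives no such rule, and its formula returns −g.

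SAP 7.1 does mention the day of discontinuation, which could be read as the drug stop. The same sentence then fixes the calculation at period duration times 2, so the wording is at best ambiguous.

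A reader might infer that compliance is understated for every child with g > 0. The documents do not support that. Where a family stops on its own, the period-based denominator counts real missed doses, and noncompliance is itself a withdrawal criterion (Protocol 6.3, item 3). Moving the end point to the last dose for everyone would make such a child look 100% compliant.

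A reader might also cap g at 13 days, because Safety Follow-Up falls 2 weeks after the final dose. That fails for liver-injury stops: Protocol 6.3.1 holds the child in the study until investigation and monitoring are complete.

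**Conclusion.** The point holds as a minor derivation error. With g > 0 days between the last dose and the first EDV, exposure in the preceding period is overstated by g. An untapered child above the minimum dose also gets −g days of Down-Titration exposure, in a period that starts after it ends if there is a single EDV. By-period compliance is understated only for instructed stops.

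The size rests on g, which is unknown, and on full dosing up to the stop. If the last dose falls on the EDV day, nothing is wrong.

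A reader might infer that the study's exposure or efficacy results are at risk. They are not. Overall exposure and Overall Period compliance end at the last dose, the exposure summary tables use whole-study exposure, and SAP compliance feeds no analysis set or test. The effect is confined to by-period listings and the by-period compliance summary.

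**What to change.** 1. **SAP 3.2.1.2, both rule sets.** Open a Down-Titration Period only when study drug dosing after the first EDV, or after Visit 6, is recorded. Otherwise start Safety Follow-Up the day after the preceding period ends.
2. **SAP 10.1.1.** Compute period exposure as the overlap of the period with the interval from first to last dose, with a minimum of 0.
3. **SAP 7.1.** Define the day of discontinuation as the date of the instructed drug stop. Keep the period-based denominator when dosing stopped without instruction.

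For a last dose on Day 22 and an EDV on Day 29, this gives 22 days of Evaluation exposure, no Down-Titration Period unless later dosing is recorded, and compliance of 100% for an instructed stop or 75.9% for an uninstructed one.

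The cost is a few lines of SAP text and no protocol change. Items 1 and 2 use the last-dose date and dosing log already collected. Item 3 also needs a rule for telling instructed from uninstructed stops. The recorded reason for discontinuation and the action taken on the adverse event form are natural sources, and the rule could be settled at the data evaluation meeting.
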